#### 7.4. Vital Signs

Vital signs (oxygen saturation, systolic and diastolic BP, orthostatic systolic and diastolic BP, pulse rate, orthostatic pulse rate, respiratory rate, and oral temperature) will be summarized as outlined in [Table 9](#). Based on the criteria in Table 8, the number and percentage of participants who had observed values and changes from baseline of clinical interest in vital sign parameters will be presented by treatment group.

Table 8. Criteria for Values of Clinical Interest in Vital Signs

Parameter	Flag	Criteria a	
		Observed Value	Change From Baseline b
Seated systolic blood pressure, mmHg	High	$\geq 180$	Increase of $\geq 10\%$ , $\geq 20\%$
	Low	$\leq 90$	Decrease of $\geq 10\%$ , $\geq 20\%$
Seated diastolic blood pressure, mmHg	High	$\geq 105$	Increase of $\geq 10\%$ , $\geq 20\%$
	Low	$\leq 50$	Decrease of $\geq 10\%$ , $\geq 20\%$
Seated pulse rate, bpm	High	$\geq 110$	Increase of $\geq 10\%$ , $\geq 20\%$
	Low	$\leq 50$	Decrease of $\geq 10\%$ , $\geq 20\%$
Seated O 2 saturation, %	High	NA	NA
	Low	<85%	NA
Oral temperature, C°	High	38°	NA
	Low	36°	NA
Respiratory rate, breaths per minute	High	18	NA
	Low	8	NA

NA=not applicable.

a A post baseline value is considered as clinical interest if it meets both the observed-value and the change-from-baseline criteria.

b Baseline is defined as the last non-missing measurement before administration of study treatment on Day 1 of the Double-blind Treatment Period

This document is confidential.

Table 9. Vital Signs Summaries

Endpoint	Description	Timing	Summary Method
Values of Clinical Interest Findings	Summarized by Vital Signs Measure. See Table 8 . (Participants meeting observed value criteria at Baseline are excluded.) 	First dose of study drug through last Vital Signs measure	Categorical summary
Descriptive	

Summary Vital Sign measures at each timepoint measured

Change from baseline in trough measurements

Change from predose to each postdose measurement at each visit (where applicable)

	Day 1, Week 1, Week 4, 8, 12 (EOT), F/U Visit	Continuous summary

EOT=end of treatment; F/U=follow-up

[1] Applies to Seated O2 saturation, oral temperature, and respiratory rate only.

Orthostatic changes in systolic BP, diastolic BP, and pulse will be summarized for each treatment group. An orthostatic measurement is obtained by subtracting the seated measurement from the standing measurement.

The number and percentage of participants who meet the following criteria for changes of clinical interest at any postdose time point (including unscheduled assessments) will also be summarized by treatment group:

1. Orthostatic decrease in systolic BP of >20 mmHg from seated to standing
2. Orthostatic decrease in systolic BP of 10% and 20% from seated to standing
3. Orthostatic decrease in diastolic BP of >10 mmHg from seated to standing
4. Orthostatic decrease in diastolic BP of 10% and 20% from seated to standing
5. Orthostatic increase in pulse of >30 bpm from seated to standing
6. Orthostatic decrease in pulse of 10% and 20% from seated to standing

All vital sign data will be listed, including the flag for values of clinical interest.

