3.5.4.2 Uptitration (Week 1 and Week 4 Visits) during the Treatment Period

At the Week 1 (Day 8 ±1) Visit during the Treatment Period, patients will begin taking the uptitrated doses as noted in [Table 2](#) in the clinic *unless*: their seated systolic BP is <90 mmHg, their standing heart rate is >20 bpm greater than baseline, or they have unresolved AEs that, in the Investigator's opinion, should preclude uptitration.

- If a patient *does* uptitrate at the Week 1 Visit to 12 mg QD, the patient will be considered for uptitration to 18 mg QD at the Week 4 Visit (Day 29 ±3) based on the criteria listed above.
- If a patient *does not* uptitrate at the Week 1 Visit to 12 mg QD, the patient will remain on 6 mg QD and will be re-assessed at Week 4 for titration to 12 mg QD. If he/she is then uptitrated to 12 mg QD at Week 4, he/she will remain on 12 mg QD for the remainder of the study. If the patient does not meet criteria for uptitration to 12 mg QD at Week 4, he/she will remain at the 6-mg dose for the remainder of the study.

On the day after any uptitration or dose adjustment, preferably in the afternoon, the patient will receive a phone call for AE and concomitant medication assessments. Additional phone calls will be conducted per the [Schedule of Events](#).

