3.8.8.5 Adverse Events of Special Interest (AESIs)

Based on the mechanism of action of sGC and anticipated vasodilation effects, the Sponsor will collect AESIs related to symptomatic or Grade ≥ 2 per NCI-CTCAE hypotensive events and/or tachycardia AEs. In addition, based on the prescribing information for riociguat (23, 24), bleeding events, pulmonary edema, and bone-related events, including fractures, will also be categorized as AESIs. The specific list of terms will be provided in the safety management plan and statistical analysis plan (SAP).

This classification means that although these events might be nonserious, they will be reported to the Sponsor per the timelines of SAEs, along with a causality assessment and an event narrative.

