## 7.5. ECG 12-Lead Electrocardiogram (ECG)

12-lead ECG measurements will be performed at the scheduled time points, including the heart rate (HR), QT interval, RR interval, PR interval, or QTcF – Fridericia's Correction Formula. ECG overall result will also be collected on the electronic case report form (eCRF). If QTc result is outside of normal range, perform in triplicate and calculate the average. If ECG result is clinically abnormal, repeat.

This document is confidential.

Descriptive statistics for ECG parameters and changes from the baseline (Day 1) values at Week 1 and the end of treatment (EOT) visit will be presented by treatment group for the Safety Population. Change from predose to postdose for ECG parameters will also be calculated for the Day 1, Week 1, and EOT visits and summarized by treatment group. For ECG triplicates, the mean will be presented as the participant's value at a given visit.

The number and percentage of participants with absolute QTcF intervals in the following categories will be tabulated by treatment group: QTcF  $\leq$  450 ms, 450 ms  $<$  QTcF  $\leq$  480 ms, 480 ms  $<$  QTcF  $\leq$  500 ms, and QTcF  $>$  500 ms. Shift tables will be presented comparing values between baseline and Week 1 and EOT.

The number and percentage of participants with absolute HR in the following categories will be tabulated by treatment group:  $\leq$  50 bpm, 50 bpm  $<$  HR  $<$  110 bpm, and HR  $\geq$  110 bpm. Shift tables will be presented comparing values between baseline and Week 1 and EOT.

The number and percentage of participants with a change from baseline in QTcF interval according to the following categories will be examined: QTcF interval increases by more than 30 ms but not more than 60 ms, and QTcF interval increases by more than 60 ms.

Additionally, the number and percentages of participants with a change from baseline in HR according to the following categories will be examined: HR increases by more than 10 bpm but not more than 30 bpm, and HR increases by more than 30 bpm. Additionally, the number and percent of participants with a change from baseline in HR corresponding to a 20% increase or more will be calculated.

All ECG data will be listed. In addition, a listing of all AEs for participants with a QTcF increase of more than 30 ms or an HR increase of more than 30 bpm will be provided.

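### SAP 7.4 item 6 counts a fall in pulse on standing while its paired item 5 counts a rise, so a standing rise of up to 30 bpm meets no categorical pulse criterion

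*SAP*

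**What the plan says.** SAP 7.4 (Vital Signs) defines an orthostatic measurement as standing minus seated. It then lists six criteria, for each of which the number and percentage of participants meeting it at any postdose time point is tabulated by treatment group.

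- Systolic pressure: item 1 is "Orthostatic decrease in systolic BP of >20 mmHg from seated to standing" and item 2 is "Orthostatic decrease in systolic BP of 10% and 20% from seated to standing".
- Diastolic pressure: items 3 and 4 follow the same pattern, a fall of more than 10 mmHg and then a fall of 10% and 20%.
- Pulse: item 5 is "Orthostatic increase in pulse of >30 bpm from seated to standing", but item 6 is "Orthostatic decrease in pulse of 10% and 20% from seated to standing".

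SAP 11 (Changes from Analysis Planned in Protocol) does not mention item 6, and neither document explains it.

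Three other places bear on direction:

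- Protocol 3.8.8.5 cites anticipated vasodilation and makes "hypotensive events and/or tachycardia AEs" events of special interest.
- Protocol 3.5.4.2 withholds a dose step if "their standing heart rate is >20 bpm greater than baseline".
- SAP 7.5 classifies ECG heart-rate changes from baseline as increases only, and adds that the number of participants with a "change from baseline in HR corresponding to a 20% increase or more will be calculated".

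**The concern.** The two blood pressure pairs set a pattern: one absolute threshold, then percentage thresholds in the same direction. Item 6 breaks it and has the wording of items 2 and 4 with the variable changed. For a vasodilator, the postural pulse response to watch for is a compensatory rise, and the three places above all look for a faster heart rate.

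Safety and tolerability is the primary objective. The 18 mg step is taken at the Week 4 visit, and the Amendment 4/5 schedule has seated-to-standing readings predose and 1 hour postdose at Weeks 4, 8 and 12. The SAP 7.4 list is the only per-patient orthostatic pulse count in the SAP that covers those postdose readings. With item 6 as a fall, the only rise it counts is one above 30 bpm, and its percentage row tracks the opposite response.

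**Working it through.** The plan states no figure here to reproduce. The check is to apply items 5 and 6 as written, and then with item 6 read as an increase.

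**Inputs.** Thresholds and the sign convention are from SAP 7.4. Seated pulses of 60, 80 and 100 bpm are assumptions, because the documents give no pulse distribution.

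**Definitions.** Let d = standing − seated, and pct = 100 × d / seated.
- Item 5: d > 30.
- Item 6 as written: pct ≤ −10, and pct ≤ −20.
- Item 6 as an increase: pct ≥ 10, and pct ≥ 20.

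**Step 1: which rises are not counted.**

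| Seated pulse (assumed) | 10% rise | 20% rise | 30 bpm as % of seated | Rises of ≥20% meeting no pulse row as written |
|---|---|---|---|---|
| 60 | 6 bpm | 12 bpm | 30/60 = 50.0% | +12 to +30 bpm |
| 80 | 8 bpm | 16 bpm | 30/80 = 37.5% | +16 to +30 bpm |
| 100 | 10 bpm | 20 bpm | 30/100 = 30.0% | +20 to +30 bpm |

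At the 10% level the uncounted bands start at +6, +8 and +10 bpm. A rise of exactly 30 bpm is not counted; 31 bpm meets item 5.

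**Step 2: single readings.**
- Seated 82, standing 99: d = 17, pct = 17/82 = 20.7%. As written it meets neither pulse row; as an increase it meets both percentage rows.
- Seated 75, standing 100: d = 25, pct = 33.3%. Same result.
- Seated 80, standing 72: d = −8, pct = −10%. As written it meets the 10% row.

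**Step 3: comparison with the blood pressure pairs.** At illustrative seated values of 120 and 75 mmHg, the absolute cut-offs are 20/120 = 16.7% and 10/75 = 13.3%. Each lies between its own 10% and 20% rows, in the same direction. For pulse, 30 bpm is 30% to 50% of seated over the assumed range. A percentage row for a rise would therefore be the more sensitive of the two, and it is the row that is absent.

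**Step 4: direction of item 6 under a drug effect.** Item 6 is met when d ≤ −0.10 × seated (or −0.20 × seated). Suppose the drug adds a non-negative amount to d and does not lower seated pulse. The left side then rises or stays, and the right side falls or stays. No reading can newly meet the criterion, so the item 6 count can only stay the same or fall. This gives direction, not size.

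**Step 5: what else captures such a rise.**
- SAP 7.4 Table 9 summarises orthostatic pulse at each time point, with change from baseline at trough and predose-to-postdose change. SAP 5.1 defines continuous summaries as n, mean, SD, median, minimum, maximum and IQR.
- SAP 8.1 fits an ANCOVA to orthostatic pulse change from baseline at predose for Weeks 1, 4, 8 and 12. Its postdose parameters are seated values only.
- SAP 7.4 Table 8 covers seated pulse and needs an observed value as well as a change: "A post baseline value is considered as clinical interest if it meets both the observed-value and the change-from-baseline criteria".
- SAP 7.5 uses supine ECG heart rate against baseline.
- All vital signs are listed, and a rise the investigator judges clinically significant is reported as an adverse event.

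A moderate rise on standing therefore stays visible, but no other table counts patients who have one.

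**The case against.** The best case against has five parts.

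1. *The rise is already analysed.* A reader might infer that rises of up to 30 bpm drop out of the analysis. They do not, as step 5 shows. This stands and narrows the point to the categorical list. The ANCOVA is predose, however, and group summaries do not say how many patients had a given rise.

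2. *A fall may be deliberate.* Table 8 flags low seated pulse with 10% and 20% decreases, and SAP 7.5 tabulates heart rates of 50 bpm or less. It would be too strong to say that the documents care only about a rise, or that item 6 is certainly a mistake. What remains is that those rows concern seated or supine rates, no reason is given for counting a fall on standing, and the percentage row for a rise is missing either way.

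3. *The supporting text measures other things.* The uptitration rule compares standing heart rate with baseline, SAP 7.5 uses supine ECG heart rate, and the special-interest text concerns adverse events. This is right. They support direction, not a seated-to-standing threshold, and the rest of the inference rests on the symmetry of the list.

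4. *Item 6 has no observed-value floor, so 100 to 90 bpm is flagged.* That is tempting as evidence of error, but items 2 and 4 have no floor either. It follows from the list's format and carries no weight.

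5. *A 10% increase row is very sensitive.* It starts at +6 bpm for a seated pulse of 60, below the smallest rise that SAP 7.5 tabulates (more than 10 bpm). That is fair. The 20% row, starting at +12 to +20 bpm over the assumed range, is the more useful one; the 10% row simply keeps the list's format.

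The table shells were not available, so they may already carry either direction.

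**Conclusion.** The point holds as a free improvement. Item 6 is probably a wording carry-over from items 2 and 4. As written, a standing rise of up to and including 30 bpm meets no categorical pulse criterion in the orthostatic list, and the percentage row cannot show the effect of main interest.

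A reader might go further and infer that the list makes olinciguat look safer than placebo. The documents do not support that. It needs a drug effect on postural pulse, and enough placebo patients whose pulse falls by at least 10% on standing for a difference to appear; neither is known. Step 4 allows the count simply to stay the same, and item 5 still counts rises above 30 bpm.

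The consequence is confined to one descriptive safety table. The TEAE primary endpoint is unaffected. The bands in step 1 rest on assumed seated pulses of 60 to 100 bpm; that rises up to 30 bpm meet neither row does not depend on them.

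**What to change.** In SAP 7.4 item 6, change the direction from decrease to increase and state the cut-points as ≥10% and ≥20%, since the present text gives no inequality. If a fall in pulse on standing is also wanted, keep it as a separate item 7 with a sentence giving the reason. Check that the table shell agrees.

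The cost is one word and two inequality signs in the SAP, plus one line in the table program, before database lock. No new data are needed, because item 5 already uses the same seated and standing values.

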## 7.5. ECG 12-Lead Electrocardiogram (ECG)

12-lead ECG measurements will be performed at the scheduled time points, including the heart rate (HR), QT interval, RR interval, PR interval, or QTcF – Fridericia's Correction Formula. ECG overall result will also be collected on the electronic case report form (eCRF). If QTc result is outside of normal range, perform in triplicate and calculate the average. If ECG result is clinically abnormal, repeat.

This document is confidential.

Descriptive statistics for ECG parameters and changes from the baseline (Day 1) values at Week 1 and the end of treatment (EOT) visit will be presented by treatment group for the Safety Population. Change from predose to postdose for ECG parameters will also be calculated for the Day 1, Week 1, and EOT visits and summarized by treatment group. For ECG triplicates, the mean will be presented as the participant's value at a given visit.

The number and percentage of participants with absolute QTcF intervals in the following categories will be tabulated by treatment group: QTcF  $\leq$  450 ms, 450 ms  $<$  QTcF  $\leq$  480 ms, 480 ms  $<$  QTcF  $\leq$  500 ms, and QTcF  $>$  500 ms. Shift tables will be presented comparing values between baseline and Week 1 and EOT.

The number and percentage of participants with absolute HR in the following categories will be tabulated by treatment group:  $\leq$  50 bpm, 50 bpm  $<$  HR  $<$  110 bpm, and HR  $\geq$  110 bpm. Shift tables will be presented comparing values between baseline and Week 1 and EOT.

The number and percentage of participants with a change from baseline in QTcF interval according to the following categories will be examined: QTcF interval increases by more than 30 ms but not more than 60 ms, and QTcF interval increases by more than 60 ms.

Additionally, the number and percentages of participants with a change from baseline in HR according to the following categories will be examined: HR increases by more than 10 bpm but not more than 30 bpm, and HR increases by more than 30 bpm. Additionally, the number and percent of participants with a change from baseline in HR corresponding to a 20% increase or more will be calculated.

All ECG data will be listed. In addition, a listing of all AEs for participants with a QTcF increase of more than 30 ms or an HR increase of more than 30 bpm will be provided.

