17. Patient will not be able to adhere to the trial assessment schedule, or, in the clinical judgement of the Investigator, the patient is otherwise not suitable for the trial.

Note: Screening Visit assessments may take place over more than 1 day. Patients may be rescreened per Investigator judgement after consultation with the Medical Monitor. Laboratory assessments may be repeated if an error is suspected. In certain circumstances local laboratory values may be acceptable.

SCHEDULE OF EVENTS

Study Period		Screening		Treatment								F/U	
Contact Type	Visit	Visit	Visit	Call	Visit	Calls	Visit	Calls		Visit	Call	Visit	Visit
Visit Name	Screening	Run-in ^a	Random- ization	-	Week 1	-	Week 4	-	-	Week 8	-	Week 12/EOT	F/U/ EOS
Day (D)→ Procedure ↓	Day -43 to -15	Day -17 to -14	Day 1	Day 2	Day 8 ±1	Wk1 V+1D, D15±2, D22±2	Day 29 ±3	Wk4 V +1D	D43 ±2	Day 57 ±7	D71 ±2	Day 85 -7/+4	Day 113 -3/+7
ICF signed	X												
I/E confirmation	X	predose	predose										
Demographics	X												
Medical/SCD history	X												
Prior & concomitant meds & procedures	X	X	X	X	X	X	X	X	X	X	X	X	X
Physical exam ^b	X	predose	predose		predose		predose			predose		predose	X
Weight & height	W, H	W	W		W		W			W		W	W
12-lead ECG ^c	X		predose pd: 4h (±15m)		predose pd: 4h (±15m)								X
AE evaluation	X	X	X	X	X	X	X	X	X	X	X	X	X
Drug screen ^d	X												
Pregnancy test ^e	X	predose	predose		predose		predose			predose		predose	X
Urinalysis sample	X		predose		predose		predose			predose		predose	X
Oral temperature & RR	X		predose pd: 1h (±15m)		predose		predose			predose		predose	X
O ₂ saturation	X	predose	predose		predose		predose			predose		predose	X
Seated BP, pulse ^f	X		pd: 6h (±15m)		predose pd: 6h (±15m)								
Seated-to-standing BP/pulse ^g	X	X	predose pd: 1,3,6 (±15m)		predose pd: 1,3,6 (±15m)		predose pd: 1h (±15m)			predose pd: 1h (±15m)		predose pd: 1h (±15m)	X

Study Period		Screening		Treatment								F/U	
Contact Type	Visit	Visit	Visit	Call	Visit	Calls	Visit	Calls		Visit	Call	Visit	Visit
Visit Name	Screening	Run-in ^a	Randomization	-	Week 1	-	Week 4	-	-	Week 8	-	Week 12/EOT	F/U/ EOS
Day (D)→ Procedure ↓	Day -43 to -15	Day -17 to -14	Day 1	Day 2	Day 8 ±1	Wk1 V+1D, D15±2, D22±2	Day 29 ±3	Wk4 V +1D	D43 ±2	Day 57 ±7	D71 ±2	Day 85 -7/+4	Day 113 -3/+7
Clinical laboratory blood samples	X		predose		predose		predose			predose		predose	X
Genotyping blood sample (w/patient consent)			predose										

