5.9.3 ECGs

Descriptive statistics for ECG parameters and changes from the baseline values at the end of treatment visit will be presented by treatment arm for the Safety Population.

The number and percentage of patients with ECG abnormalities will be tabulated by treatment arm. Shift tables will be presented comparing values between baseline and end of study. A listing of all AEs for patients with ECG abnormalities will also be provided.

The number and percentage of patients with absolute QTcF intervals in the following categories will be examined: $QTcF \leq 450$ ms, $450 \text{ ms} < QTcF \leq 480$ ms, $480 \text{ ms} < QTcF \leq 500$ ms, and $QTcF > 500$ ms. Shift tables will be presented comparing values between baseline and end of study.

Additionally, the number and percentage of patients with a change from baseline in QTcF interval according to the following categories will be examined: QTcF interval increases by more than 30 ms, but not more than 60 ms, and QTcF interval increases by more than 60 ms. Shift tables will be presented comparing values between baseline and end of study.

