Day (D) → Procedure 	Day -43 to -15	Day -17 to -14	Day 1	Day 2	Day 8 ±1	Wk1 V+1D, D15±2, D22±2	Day 29 ±3	Wk4 V+1D ±2	D43 ±2	Day 57 ±7	D71 ±2	Day 85 -7/+4	Day 113 -3/+7
ICF signed	X												
I/E confirmation	X	predose	predose										
Demographics	X												
Medical/SCD history	X												
Prior & concomitant meds & procedures	X	X	X	X	X	X	X	X	X	X	X	X	
Physical exam b	X	predose	predose		predose		predose		predose		predose		X
Weight & height	W, H	W	W		W		W		W		W	W	
12-lead ECG c	X		predose pd: 4h (=15m)		predose pd: 4h (=15m)							X	
AE evaluation	X	X	X	X	X	X	X	X	X	X	X	X	
Drug screen d	X												
Pregnancy test e	X	predose	predose		predose		predose		predose		predose	X	
Urinalysis sample	X		predose		predose		predose		predose		predose	X	
Oral temperature & RR	X		predose pd:1h (=15m)		predose		predose		predose		predose	X	
O 2 saturation	X	predose	predose		predose		predose		predose		predose	X	
Seated BP, pulse f	X		pd: 6h (=15m)		predose pd: 6h (=15m)								
Seated-to-standing BP/pulse g	X	X	predose pd: 1,3,6 (=15m)		predose pd:1,3,6 (=15m)		predose pd:1h (=15m)		predose pd:1h (=15m)		predose pd:1h (=15m)	X	

This document is confidential.

Study Period		Screening		Treatment								F/U	
Contact Type	Visit	Visit	Visit	Call	Visit	Calls	Visit	Calls		Visit	Call	Visit	Visit
Visit Name	Screening	Run-in a	Randomization	-	Week 1	-	Week 4	-	-	Week 8	-	Week 12/EOT	F/U/ EOS
Day (D) → Procedure ↓	Day -43 to -15	Day -17 to -14	Day 1	Day 2	Day 8 ±1	Wk1 V+1D, D15±2, D22±2	Day 29 ±3	Wk4 V+1D	D43 ±2	Day 57 ±7	D71 ±2	Day 85 -7/+4	Day 113 -3/+7
Clinical laboratory blood samples	X		predose		predose		predose			predose		predose	X
Genotyping blood sample (w/patient consent)			predose										
PK blood sample			predose pd: EOV		predose pd: EOV		predose pd: EOV			predose pd: EOV		predose pd: EOV	X
Urine samples for UACR		predose	predose				predose					predose	X
Blood sample for biomarkers			predose		predose		predose					predose	X
Blood samples for platelet biomarkers b			predose pd: 5h(±15m)				predose					predose	
eDiary registration /training		predose											
eDiary device check			predose										
PROMIS Fatigue; Absences		predose	predose		pd: ≤1h		pd: ≤1h			pd: ≤1h		pd: ≤1h	
ASCOQ-Me		predose			pd: ≤1h		pd: ≤1h			pd: ≤1h		pd: ≤1h	
PGIC												pd: ≤1h	
EQ-5D-5L & SF-12v2		predose	predose									pd: ≤1h	X
Randomization			X										

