#### 5.4. Visit Windows

The following algorithms will be used to map the analysis visit for the on-treatment analysis.

Analysis Visit	Mapping Window (Study Day)
Week 1	Day 7 to Day 14
Week 4	Day 15 to Day 36
Week 8	Day 37 to Day 64
Week 12	Day 65 to (last dosing date + 4 days)

End of Treatment (EOT) analysis visit is defined as the last measurement taken that is on-treatment. For all endpoints other than TEAEs, 'on-treatment' is defined as the first dosing date through 4 days after the end of treatment visit (the last dosing date + 4 days).

Last dosing date needs to be considered for all mappings. eg, if participant comes in for Week 8 but is more than 4 days out of last dosing, then that visit will not be mapped to Week 8 for analysis as the participant is not 'on-treatment'.

If multiple measures are mapped to same analysis visit, the last set of records will be included in the analysis. In listings, data will be presented with visit collected, analysis visit mapped, and analysis flag.

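### The SAP plans end-of-treatment ECG and QTcF tables, but no ECG is scheduled at Week 4, 8 or 12, so those tables would show Day 8 data and no on-drug ECG at 18 mg

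*SAP*

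**What the plan says.** SAP 7.5 plans "Descriptive statistics for ECG parameters and changes from the baseline (Day 1) values at Week 1 and the end of treatment (EOT) visit" by treatment group. It adds that "Change from predose to postdose for ECG parameters will also be calculated for the Day 1, Week 1, and EOT visits". For the QTcF and heart-rate categories, "Shift tables will be presented comparing values between baseline and Week 1 and EOT".

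SAP 5.4 fixes the meaning of the label: "End of Treatment (EOT) analysis visit is defined as the last measurement taken that is on-treatment". For everything except TEAEs, on-treatment "is defined as the first dosing date through 4 days after the end of treatment visit (the last dosing date + 4 days"). SAP 5.1 keeps unscheduled and repeat assessments out of the summary tables and puts them in listings only.

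Protocol 5.9.3 has the same expectation for change from baseline: "Descriptive statistics for ECG parameters and changes from the baseline values at the end of treatment visit will be presented by treatment arm". Its shift tables, however, run from baseline to end of study, not to end of treatment.

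In the Protocol Schedule of Events the 12-lead ECG row has the entry "predose pd: 4h (±15m") at Randomization and again at Week 1, plus single entries at Screening and at Follow-up. SAP Table 5a (Amendment 3) and Table 5b (Amendments 4 and 5) show the same four visits.

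**The concern.** The analysis asks for ECG data from a visit at which the schedule collects none. SAP 5.4 does not leave the cells blank. It fills them with the most recent on-treatment value, which is the Week 1 ECG. The Week 1 and end-of-treatment columns would then largely repeat each other, and the end-of-treatment predose-to-postdose change would have no data of its own.

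The stakes are highest in the arm labelled 18 mg. SAP Tables 7 and 9 equate end of treatment with Week 12, so a reader would take an end-of-treatment QTcF column for that arm as data at Week 12 on 18 mg. It would in fact predate any 18 mg dose. Safety and tolerability are the primary objective. SAP 7.2 itself lists adverse events of Weeks 1, 2 and 5 separately so that the dose steps can be told apart, so attribution to dose step evidently matters to the plan.

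The QTcF criterion for stopping study drug in Protocol 3.4.2 meets the same gap: after Week 1 no scheduled on-drug ECG supplies a value for it.

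**Working it through.** The documents give no figure to reproduce here. The check is a reading of the schedules followed by day arithmetic.

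**1. Where the ECGs fall.** The ECG and physical-examination rows of the Protocol Schedule of Events each have 13 cells, so they can be compared column by column.

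| Visit | Physical examination | 12-lead ECG |
|---|---|---|
| Screening | yes | yes |
| Run-in | predose | none |
| Randomization, Day 1 | predose | predose and 4 h postdose |
| Week 1, Day 8 ±1 | predose | predose and 4 h postdose |
| Week 4, Day 29 ±3 | predose | **none** |
| Week 8, Day 57 ±7 | predose | **none** |
| Week 12/EOT, Day 85 −7/+4 | predose | **none** |
| Follow-up | yes | yes |

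The physical-examination row fills Weeks 4, 8 and 12, so shifted columns do not explain the gap. SAP Tables 5a and 5b agree. Table 5b is partly broken in extraction, but its last ECG entry lines up with the Follow-up entries for weight and pregnancy test. The early-termination visit (Protocol 3.4.3) adds nothing, because it asks for the end-of-treatment assessments and these include no ECG.

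**2. Can the Follow-up ECG serve as end of treatment?**
- Follow-up is 28 (−3/+7) days after the last dose (Protocol 3.2): 28 − 3 = 25 to 28 + 7 = 35 days.
- The on-treatment limit is the last dose + 4 days (SAP 5.4).
- Smallest shortfall: 25 − 4 = 21 days outside the window. It cannot.

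**3. What the rule selects.** With unscheduled ECGs excluded (SAP 5.1) and Follow-up excluded (step 2), the last on-treatment ECG is the Week 1 4 h reading, on Days 7 to 9.

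**4. Distance from the 18 mg step** (Protocol 3.5.4.2: Week 4 Visit, Day 29 ±3, so Days 26 to 32).
- Shortest gap: 26 − 9 = 17 days
- Longest gap: 32 − 7 = 25 days
- Nominal gap: 29 − 8 = 21 days

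For participants who uptitrate on schedule, the Week 1 predose ECG is on 6 mg and the 4 h ECG follows the first 12 mg dose.

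**5. Size of the gap, nominal schedule.**
- Treatment days after the last scheduled on-drug ECG: 85 − 8 = 77; 77/85 = 91%
- Days at the 18 mg step: 85 − 29 + 1 = 57; 57/85 = 67%
- Scheduled ECGs on those 57 days: 0
- Planned participants in that arm: 48 × 3/4 = 36

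**6. Protocol against SAP.** The protocol's shift tables run to end of study, the Follow-up visit, where an ECG exists. The SAP moves them to Week 1 and end of treatment, where the second does not. SAP Section 2 requires changes from the protocol's planned analyses to be recorded in Section 11, which lists only the work and school absence endpoint.

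**The case against.** The mismatch with the schedule is hard to dispute. The case on the other side concerns its reach and weight.

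- **A second reading of end of treatment.** SAP 7.5 speaks of the end-of-treatment visit, and SAP Tables 7 and 9 attach that label to Week 12. If the tables were programmed on the nominal visit, the cells would be empty rather than filled with Day 8 data, and nobody would be misled. This is fair as a description of an alternative, but SAP 5.4 defines the term explicitly and the other way. Either reading leaves an analysis that cannot be delivered.
- **Unscheduled ECGs.** A participant could have an unscheduled ECG on 18 mg. It would appear in listings only, so the statement about the summary tables stands. The gap is in scheduled ECGs.
- **Schedules not seen.** Those for the original protocol through Amendment 2 are not reproduced; SAP 3.8 calls the differences minor. They do not govern the 18 mg arm.
- **Not every participant fits.** The figure of 36 is planned, not actual. Some participants will not uptitrate and will never take 18 mg. Someone whose last dose was more than 4 days before the Week 1 ECG would contribute a Day 1 postdose reading. These points soften the count, not the conclusion.
- **The column label.** SAP 5.1 defines the 18 mg column by randomized regimen, not by dose at measurement. That is accurate, but it does not tell the reader that an end-of-treatment value came from Day 8.
- **Importance.** The primary endpoints are TEAEs, and the ECG summaries are descriptive with no test attached. That limits the effect on inference. The tables still belong to the safety assessment that answers the primary objective.

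**Conclusion.** The concern holds. As written, the end-of-treatment ECG tables would carry Week 1 data under a later label, and for the 18 mg arm they would contain no on-drug measurement at 18 mg. On the nominal schedule all 57 days at that step and 77 of 85 treatment days (91%) lack a scheduled ECG, for about 36 planned participants.

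This rests on three things: the schedules for Amendments 3, 4 and 5 as shown; the SAP 5.4 definition being applied; and unscheduled ECGs staying out of summary tables under SAP 5.1. If the nominal Week 12 visit were used instead, the tables would be empty. The gap at the target dose is specific to Amendment 4 and later. In the 2, 4 and 6 mg arms the full dose follows Week 1, so the Week 1 ECG falls at about the first full dose, although the end-of-treatment label is equally wrong there.

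**What to change.** Reconcile SAP 7.5, SAP 5.4 and Protocol 5.9.3 with the Schedule of Events. With the schedule as it stands:

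1. Delete the end-of-treatment ECG outputs from SAP 7.5: descriptive statistics, change from baseline, predose-to-postdose change, and the QTcF and heart-rate shift tables.
2. Label the Week 1 ECG by the dose actually taken. For participants under Amendment 4 or later who uptitrate on schedule, that is predose on 6 mg and 4 h after the first 12 mg dose.
3. Report the Follow-up ECG in its own column as off drug, 25 to 35 days after the last dose. This also restores the protocol's baseline-to-end-of-study shift.
4. State in the SAP and the report that no ECG was scheduled on 18 mg, so QTcF conclusions do not extend to that dose. Show any unscheduled ECG in the listings with study day and dose.
5. Record the departure from Protocol 5.9.3 in SAP Section 11.

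The QTcF criterion in Protocol 3.4.2 and the ECG schedule should also be reconciled by those responsible for clinical conduct.

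The cost is SAP wording and table-shell relabelling, with no new data. The price is a narrower QTcF safety statement, which is all the scheduled ECGs can support.
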